2. INTRODUCTION

2.1. Study Rationale

The International Council for Harmonisation (ICH) E14 guidance, as adopted in the US Food and Drug Administration (FDA) Guidance for Industry, E14 Clinical Evaluation of QT/QTc Interval Prolongation and Proarrhythmic Potential for Non-Antiarrhythmic Drugs [DHHS, 2005], emphasizes the need to obtain clear and robust data through “thorough” studies that assess the effect of new chemical entities on electrocardiogram (ECG) parameters. Specifically, “thorough” studies are defined as trials dedicated to evaluating a compound’s effect on cardiac repolarization, as measured by the corrected QT interval (QTc). Although many Phase 1, 2, and 3 studies may be conducted with a new compound, they typically utilize insufficient sample sizes, infrequent sampling of ECG data, or inadequate controls to overcome high variance in cardiac repolarization due to spontaneous change. Therefore, this thorough QT (TQT)/QTc study will be conducted to evaluate the effect of GSK3640254 on cardiac repolarization.

2.2. Background

GSK3640254 is a next-generation human immunodeficiency virus (HIV)-1 maturation inhibitor (MI) which binds near a key structural element within the group-specific antigen (Gag) polyprotein that is required for virion maturation and assembly. Maturation inhibitors block the last protease cleavage event between Gag protein segments designated as 24-kilodalton HIV capsid protein p24 and spacer peptide 1. Blockage at this step results in the release of immature non-infectious virus particles. Other small molecules within this class have demonstrated a PK/pharmacodynamic (PD) relationship and longer-term efficacy through Phase 2a to 2b studies.

At the time of this protocol submission, GSK has completed a Phase 2a study (short-term, monotherapy, proof of concept) on GSK3640254. Additionally, the safety, tolerability, and PK have been evaluated in 7 other completed Phase 1 studies in healthy volunteers up to a maximum dose of 320 mg daily for 14 days. The totality of the clinical data shows: 1) GSK3640254 is generally well-tolerated in short-term studies, and 2) GSK3640254 has a short-term PK/PD (decline in HIV-1 RNA) relationship. Summaries of the preclinical and clinical studies are included in the Clinical Investigator's Brochure (CIB) [GlaxoSmithKline (GSK) Document Number [2018N379610_01](#), 2019].

2.2.1. Key Safety Data with a Prior Maturation Inhibitor (GSK3532795)

Previously, ViiV Healthcare (VH) studied a structurally similar MI, GSK3532795, in the Phase 2b study, Study 205891 (maximum dose 180 mg daily). The Week 24 primary endpoint analysis showed GSK3532795 was not optimal for Phase 3 development due to gastrointestinal (GI) intolerance and treatment-emergent resistance. Specifically, a relatively higher rate of GI intolerance (predominately Grade 1 to 2 diarrhoea in 38% to 61% of participants and abdominal pain in 8% to 22% of participants) and higher rate of nucleoside reverse transcriptase inhibitor resistance (6.5%) with clinically significant changes in GSK3532795 susceptibility were observed across all three GSK3532795

treatment arms [Morales-Ramirez, 2018]. Given these clinical and tolerability issues, the sponsor terminated Study 205891 and did not advance GSK3532795 into Phase 3 studies.

Aside from mild to moderate GI intolerance, 2 serious adverse events (SAEs) occurred in the Phase 1 TQT study AI468044/206220 [Bristol-Myers Squibb, 2017] at supratherapeutic doses: 1 healthy participant had an episode of acute psychosis and another had suicidal ideation/homicidal ideation as diagnosed through an interview by a psychiatrist. The 2 participants received GSK3532795 at 240 mg twice daily (BID) and 240 mg once daily (QD) with food, respectively. These events were assessed as related to study drug but were not observed in any other clinical study with GSK3532795. The most frequent neuropsychiatric adverse events (AEs) in studies with GSK3532795 were headache, dizziness, and sleep abnormalities (e.g., insomnia, abnormal dreams).

Importantly, neither of these GI or psychiatric safety findings have been reproduced in the completed clinical studies of GSK3640254 in healthy volunteers or HIV-1 infected treatment-naïve participants.

2.2.2. Preclinical Summary with GSK3640254

2.2.2.1. Pharmacokinetics and Product Metabolism in Animals

Following intravenous administration, GSK3640254 exhibited low systemic clearance, high volume distribution, and elimination half-lives of 5.06, 4.0, 18.7, and 5.3 hours in mouse, rats, dogs and monkeys, respectively. GSK3640254 was eliminated mainly by direct glucuronidation followed by biliary excretion in bile-duct cannulated rats.

Following repeat oral administration in the rat and dog, increases in systemic exposure to GSK3640254 was generally sub-proportional with dose. There was no or minimal accumulation of GSK3640254 after repeat dosing, and no consistent indication of a difference in exposure between genders. Metabolic pathways observed in vitro included mono-oxidation, N-dealkylation, and direct glucuronidation, with no unique metabolites generated in human liver microsomes or hepatocytes. In rat and dog plasma, GSK3640254 was either the only or the predominant drug-related component with minor oxidative metabolites.

Based on the predicted systemic exposures in humans, there is a potential risk for GSK3640254 to act as a perpetrator of drug-drug interactions (DDIs) of substrates of organic anion-transporting polypeptide 1B3 and multi-drug resistance protein 2. GSK3640254 was an inhibitor of uridine diphosphate glucuronosyltransferase (UGT) 1A1 and clinical DDI via this mechanism could be possible.

2.2.2.2. Toxicology in Animals

The primary target organ of toxicity in non-clinical studies with GSK3640254 was the stomach, with microscopic changes affecting parietal and chief cells in both rats and dogs. Due to microscopic changes in the stomach of rats at the lowest dose tested after 26 weeks, a no observed adverse effect level (NOAEL) in rats was unable to be determined. Microscopic findings in the stomach of rats were minimal to mild at the lowest observed adverse effect level (LOAEL) of 10 mg/kg/day (area under the plasma concentration-time curve [AUC] = 18.9 µg·hr/mL), corresponding to 0.63-fold the

measured highest mean human exposure in the planned Phase 2b clinical study. Following 39 weeks of dosing in dogs, the NOAEL for microscopic changes in the stomach was 0.2 mg/kg/day, and exposures were 0.28-fold the highest mean clinical exposure. Microscopic stomach changes were associated with increases in serum gastrin when evaluated in the 26- and 39-week studies in rats and dogs, respectively. All microscopic findings in the stomach of rats and dogs and changes in serum gastrin were shown to be partially reversible following a 4-week recovery period. Microscopic findings in the stomach were minimal to mild at the LOAELs of 10 mg/kg/day (AUC = 18.9 µg.hr/mL) and 1 mg/kg/day (AUC = 46.4 µg/hr/mL) in rats and dogs, respectively, corresponding to 0.63-fold and 1.6-fold highest mean clinical exposure in the planned Phase 2b clinical study. Potential effects in the stomach of humans during clinical studies are being investigated in a gastric safety sub-study.

With correction for protein binding, compared to the half maximal inhibitory concentration for the hERG/IKr potassium channel, there is a 7.9-fold margin above the predicted average clinical maximum observed concentration (Cmax) exposure for the highest dose planned in this study. Exposure where a minimal increase in QT interval was seen in a single dog in the single dose safety pharmacology study in telemeterized dogs was 1.8-fold higher than the predicted Cmax at the highest planned dose in this study. In addition, there were no effects on ECG parameters in dogs given up to 25 mg/kg/day for 4 weeks at 9.75-fold above the predicted average Cmax at the highest dose in this study.

2.2.3. Summary of GSK3640254 Clinical Pharmacokinetics

Pharmacokinetic data for clinical studies performed to date are summarized as follows:

- Following single oral doses from 1 to 700 mg, AUC from time zero extrapolated to infinity, and Cmax tended to increase in a dose-proportional manner through 100 mg. Higher doses showed a less than dose-proportional increase in exposure and there was no apparent increase in exposure from 400 to 700 mg.
- Following multiple-dose administration over 50 to 320 mg dose range for 14 days with a moderate-fat meal in the single-ascending dose (SAD)/multiple-ascending dose (MAD) first-time-in-human (FTIH) Study 207187:
 - Median time of maximum observed concentration (Tmax) ranged between 3.8 to 4.3 hours.
 - The mean half-life ranged from approximately 22 to 28 hours.
 - There was a slightly less than dose-proportional increase in Cmax and AUC from time zero to the end of the dosing interval at steady state (AUC[0- τ]) from 50 to 320 mg QD.
 - The exposure on Day 14 was, on average, 1.9- to 2.3-fold higher for Cmax and 2.2- to 2.6-fold higher for AUC(0- τ) compared to those on Day 1.

- PK variability (between-subject variability) was modest, and ranged from 8% to 50%.
- Coadministration with food increases overall GSK3640254 exposure 2- to 4-fold; therefore, GSK3640254 is recommended to be taken with food.
- There was no clinically meaningful drug interaction between GSK3640254 and either tenofovir alafenamide/emtricitabine (Study 208134) or dolutegravir (Study 209712).

Additional information regarding clinical PK data can be found in the CIB [GSK Document Number [2018N379610_01](#), 2019].

2.2.4. Summary of GSK3640254 Metabolism

With recombinant cytochrome P450 (CYP) enzymes, GSK3640254 was mainly metabolized by CYP3A4/3A5, CYP2C9, CYP1A2 and CYP2C8. GSK3640254 was stable in recombinant UGT enzymes. In rat and dog plasma, GSK3640254 was either the only or the predominant drug-related component with minor oxidative metabolites (e.g., hydroxylation and N-dealkylation). Preliminary analysis of bile samples of bile-duct cannulated rats dosed with unlabeled GSK3640254 suggested that GSK3640254 was eliminated mainly by direct glucuronidation followed by biliary excretion in rats. In human plasma, GSK3640254 was the predominant drug-related component with low levels of oxidative metabolites as shown by preliminary human metabolism study following repeat oral doses of 320 mg/day. Additional information regarding GSK3640254 metabolism can be found in the CIB [GSK Document Number [2018N379610_01](#), 2019].

2.2.5. Summary of GSK3640254 Safety

A summary of safety data from 7 Phase 1 studies and a Phase 2a study performed to date is summarized below:

- No deaths or treatment-related SAEs have been reported during clinical studies with GSK3640254.
- The majority of AEs were **CCI** (Grade 1).
- Treatment-related dermatologic AEs (including AEs leading to study discontinuation) included rash, drug eruption, pruritis, urticaria, and maculopapular rash. Adverse events of urticaria and maculopapular rash led to discontinuation.
- Treatment emergent drug-related Grade 2 AEs included the following: headache (2 participants; one participant each in Studies 207187 and 208132), nausea (2 participants; one participant each in Studies 208134 and 208132), and abdominal pain (1 participant in Study 208132).

- Clinically notable AEs of elevated transaminases occurred in Studies 207187 (SAD/MAD, n = 1 healthy participant [17%], Grade 1) and 208135 (DDI with oral contraceptive Portia [ethinyl estradiol/levonorgestrel], n = 8 healthy participants [35%], 3 Grade 1 and 5 Grade 2). Subsequent analysis in Study 208135 showed no PK/PD relationship with either GSK3640254 or Portia and elevated transaminases. The elevated transaminases were likely due to the recent initiation of hormonal contraception in study participants.
- Treatment-related AEs reported in more than 1 study included headache (Studies 207187, 208131, and 208132) and nausea (Studies 207187 and 208132).
- Across studies, the most common AEs regardless of grade, relationship, and concomitant medication administration were headache (11.9%), contact dermatitis and related events (7.8%), diarrhoea (5.5%), and abdominal pain (4.1%).
- Across studies, low grade GI intolerance has been observed; the majority were mild. Both Study 207187 (SAD/MAD) and Study 208312 (proof of concept) are relevant to this study given dosing of 7 to 14 days; most AEs in Study 207187 were unrelated and most AEs in Study 208132 were related.
- Across studies, there were generally no clinically significant changes in vital sign measurements, ECG results, or safety laboratory parameters (other than the elevated transaminases due to Portia, noted above). Specifically, no participant has demonstrated QT prolongation: absolute value >500 ms, or increase from baseline >60 ms.

The full safety profile for GSK3640254 can be found in the CIB [GSK Document Number [2018N379610_01](#), 2019].

2.2.5.1. Cardiac Safety

A cardiodynamic evaluation of healthy participants in the MAD portion of Study 207187 [GSK Document Number [2020N430256_00](#)] (placebo or GSK3640254 dose range 50 to 320 mg daily for 14 days) was performed. Serial ECGs were extracted from continuous Holter monitors at time-matched baseline on Day -1 and for approximately 24 hours post-dose on Days 1 and 14. There were no abnormal clinically significant arrhythmias or QT prolongations (values >500 ms or increases >60 ms from baseline) observed for any participant in the SAD or MAD cohorts. In the concentration-corrected QT interval (C-QTc) analysis, a final model with a treatment effect-specific intercept reasonably represented the data. The slope of the C-QTc relationship was 0.004 ms per ng/mL (90% confidence interval [CI]: 0.0023 to 0.0048) with a small treatment effect-specific intercept of -0.9 ms (90% CI: -4.47 to 2.69). The QT effect (placebo-corrected change from baseline in QTcF [$\Delta\Delta\text{QTcF}$]) of GSK3640254 could be predicted to be 5.38 ms (90% CI: 1.66 to 9.10) and 6.70 ms (90% CI: 2.79 to 10.61) for the 200 mg (1779 ng/mL) and 320 mg (2154 ng/mL) doses, respectively, on Day 14. Based on this C-QTc analysis, a QTc using the Fridericia formula (QTcF) effect above 10 ms could be excluded in GSK3640254 plasma concentrations of up to approximately 2000 ng/mL (corresponding to doses approximately \leq 200 mg QD).

2.3. Benefit/Risk Assessment

Based upon preclinical and clinical studies (including the prior MI GSK3532795), the potential risks for GSK3640254 are GI intolerance (e.g., abdominal pain and diarrhoea) and gastric toxicity (effects on parietal cell and chief cells), prolongation of QTc, neuropsychiatric safety, and rash.

Gastrointestinal intolerance will be assessed using clinical monitoring as outlined in Section 8.2.6.

Prolongation of the QTc interval is a risk. One preclinical study showed 1 dog with an increased QTc interval when given a single dose of GSK3640254. A cardiodynamic analysis of healthy participants in Study 207187 was conducted and summarized in Section 2.2.5.1. Importantly, in GSK3640254 clinical studies to date, there have been no abnormal clinically significant arrhythmias, and no participants met the study-based QTc stopping criteria for QTcF prolongations: values >500 ms or increases >60 ms from baseline. This study contains specific cardiac exclusion criteria (Section 5.2), has ECG monitoring (at Tmax once GSK3640254 attains steady state concentration [Section 1.3]), and has QTcF-based stopping criteria (Section 7.1.2).

Given the risk of psychiatric events as seen with GSK3532795 (Section 2.2.1), the protocol will exclude potential participants with any significant pre-existing psychiatric condition or positive (abnormal) response on the Columbia-Suicide Severity Rating Scale (C-SSRS; Section 5.2). Participants will also be required to provide response to the C-SSRS during the on-treatment portion of the study and will be clinically evaluated for suicidality as indicated (Section 1.3 and Section 8.2.5).

Across clinical studies, AEs leading to discontinuation have included urticaria and maculopapular rash. This study includes individual participant stopping criteria for any Grade 3 or higher rash or Grade 2 rash with evidence of systemic involvement or any allergic or hypersensitivity reactions (Section 7.1.4).

To ensure the overall safety of participants (including, but not limited to, the risk of GI intolerance, QTc prolongation, neuropsychiatric safety, and rash), this clinical study will include healthy adults who will receive clinical, ECG, and laboratory evaluations during their participation while confined to the clinic. More detailed information about the known and expected benefits and risks and reasonably expected AEs of GSK3640254 may be found in the CIB [GSK Document Number 2018N379610_01, 2019].

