12-lead ECG	X	X	X			X			X		X	The pre-dose ECG on Day 1 will be collected in triplicate. Other ECGs will be single. The ECGs on Days 1, 4, and 7 will be collected at pre-dose and post-dose at 2, 4, and 6 hours.
Drug, alcohol, and cotinine screen	X											See Appendix 2 for specific tests to be performed.

Procedure	Check-in	Baseline	Treatment							Follow-up		Notes
	Day -2	Day -1	Day 1	Day 2	Day 3	Day 4	Day 5	Day 6	Day 7	Day 8	Day 9 ¹	
Molecular Test for SARS-CoV-2	X ¹							X			X	¹ This second test should be performed 24 hours prior to admission to the unit. Participants should be quarantined within the unit until the second test result is negative. Once the second test result is confirmed to be negative, they can be released into the unit and follow infection control practices.
Laboratory assessments (haematology, chemistry, urinalysis)	X				X				X		X	See Appendix 2 for specific tests to be performed.
Pregnancy test	X										X	Serum testing on Day -1.
Columbia-Suicide Severity Rating Scale	X			X		X		X		X		
Randomization			X									
Study intervention: Sentinel Cohort 1: GSK3640254 500 mg or placebo once daily Sentinel Cohort 2 (optional): To be determined after completion of Cohort 1 and not to exceed 500 mg BID.			X	X	X	X	X	X				

Procedure	Check-in	Baseline	Treatment							Follow-up		Notes
	Day -2	Day -1	Day 1	Day 2	Day 3	Day 4	Day 5	Day 6	Day 7	Day 8	Day 9 ¹	
GSK3640254 PK sampling			X				X	X	X	X	X	Blood collection for PK analysis of GSK3640254 will be collected within 40 minutes prior to the morning dose on Days 1, 5, 6, and 7, and after dosing on Day 7 at 0.5, 1, 2, 3, 3.5, 4, 4.5, 5, 6, 12, 24, and 48 hours.
AE review	←-----X-----→											
SAE review	←-----X-----→											
Concomitant medication review	←-----X-----→											

AE = adverse event; D = day; ECG = electrocardiogram; PK = pharmacokinetic; SAE = serious adverse event.

1. Evaluations scheduled for Day 9 will also be performed for participants who discontinue early.

Screening Visit – Part 2, Thorough QT Study

Procedure	Screening (up to 29 days before Day -2)
Informed consent	X
Inclusion and exclusion criteria	X
Demography	X
Full physical examination including height and weight ¹	X
Laboratory assessments (hematology, chemistry, urinalysis)	X
12-lead electrocardiogram	X
24-hour Holter monitor recording ²	X
Vital sign measurements	X
Medication/drug/alcohol history	X
Past and current medical conditions	X
Columbia-Suicide Severity Rating Scale	X

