Serum pregnancy test	X
Follicle-stimulating hormone (as needed, to confirm postmenopausal status)	X
Drug, alcohol, and cotinine screen	X
Human immunodeficiency virus, hepatitis B and C screening	X
Molecular test for SARS-CoV-2 ³	X

1. A full physical examination will include at a minimum, assessments of the skin, cardiovascular, respiratory, gastrointestinal, and neurological systems.
2. May be performed either during Screening or on Day -2 upon admission.
3. Two consecutive approved molecular tests (polymerase chain reaction or antigen test). The first test should be performed ≥ 7 days prior to admission.

Time and Events Table – Part 2, Thorough QT study

Procedure	Check -in	Baseline		Periods 1, 2, and 3							W	Period 4							Follow-up		Notes	
	D -2	D -1	D1	D2	D3	D4	D5	D6	D7	D8-14 ¹	D1	D2	D3	D4	D5	D6	D7	D8	D9 ²			
Admit to clinic	X																					
Discharge from clinic																				X	Final discharge from clinic following completion of the last study procedure on Day 9 of Period 4.	
Brief physical examination	X										D14									X	An interim symptom-targeted brief physical examination will be performed at the discretion of the investigator. See Section 8.2.1 for description of the brief physical examination.	
Vital signs	X	X	X	X	X	X	X	X	X	D8, D14 only	X	X	X	X	X	X	X	X	X	Blood pressure and pulse will be measured in triplicate pre-dose on Day 1 of each period and single blood pressure and pulse will be measured on other study days. On Day 7 of each period, blood pressure and pulse to be measured before dosing and 4 and 24 hours after dosing.		
Daily temperature check	X	X	X	X	X	X	X	X	X		X	X	X	X	X	X	X	X	X	While confined to clinic.		

Procedure	Check -in	Baseline	Periods 1, 2, and 3							W	Period 4						Follow-up		Notes	
	D -2	D -1	D1	D2	D3	D4	D5	D6	D7	D8-14 ¹	D1	D2	D3	D4	D5	D6	D7	D8	D9 ²	
Safety 12-lead ECG	X	X	X	X		X	X		X	D8, D14	X	X		X	X		X	X	X	The pre-dose ECGs on Day 1 of each period will be collected in triplicate. All other ECGs will be single. On Days 1, 4, and 7, ECGs will be collected at pre-dose and post-dose at 1, 2, 3, 4, 6, and 24 hours.
Drug, alcohol, and cotinine screen	X									D14										See Appendix 2 for specific tests to be performed. Day 14 drug, alcohol, and cotinine screen required only for participants that are furloughed during the washout period.
Laboratory assessments (hematology, chemistry, urinalysis)	X									D8, D14									X	See Appendix 2 for specific tests to be performed.

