Procedure	Check -in	Baseline	Periods 1, 2, and 3							W	Period 4							Follow-up			Notes
	D -2	D -1	D1	D2	D3	D4	D5	D6	D7	D8-14 ¹	D1	D2	D3	D4	D5	D6	D7	D8	D9 ²		
Molecular Test for SARS-CoV-2	X ¹							X		D13							X				¹ The second test should be performed 24 hours prior to admission to the unit. Participants should be quarantined within the unit until the second test result is negative. Once the second test result is confirmed to be negative, they can be released into the unit and follow infection control practices. Test to be obtained every 7 days from Check-in (regardless of period or washout) while in-house.
Pregnancy test	X									D14										X	Serum testing on Day -2. Day 14 pregnancy test required only for participants that are furloughed during the washout period.
Columbia Suicide Severity Rating Scale	X									D8									X		
Randomization			X																	Period 1 only.	
Study intervention: GSK3640254 therapeutic or supratherapeutic dose, placebo, or moxifloxacin			X	X	X	X	X	X	X		X	X	X	X	X	X	X			Moxifloxacin treatment consists of GSK3640254 placebo on Days 1 through 6 with moxifloxacin on Day 7 only.	
Holter ECG recording ³		X	X						X	D8	X						X	X			

Procedure	Check -in	Baseline	Periods 1, 2, and 3						W	Period 4						Follow-up		Notes		
	D -2	D -1	D1	D2	D3	D4	D5	D6	D7	D8-14 ¹	D1	D2	D3	D4	D5	D6	D7	D8	D9 ²	
GSK3640254 PK sampling			X				X	X	X	D8	X				X	X	X	X		Blood collection for PK analysis will be collected within 40 minutes prior to dosing on Days 1, 5, 6, and 7. Day 7 post-dose samples will be collected at 0.5, 1, 2, 3, 3.5, 4, 4.5, 5, 6, 8, 10, 12, and 24 hours.
Moxifloxacin PK sampling								X		D8						X	X			Blood collection for PK analysis of moxifloxacin will be collected within 40 minutes prior to the dose on Day 7. Day 7 post-dose samples will be collected at 0.5, 1, 2, 3, 3.5, 4, 4.5, 5, 6, 8, 10, 12, and 24 hours.
AE review			←-----X-----→																	
SAE review			←-----X-----→																	
Concomitant medication review			←-----X-----→																	

AE = adverse event; D = day; ECG = electrocardiogram; PK = pharmacokinetic; SAE = serious adverse event; W = washout.

- Participants may be furloughed during the washout portion of the respective period following Day 8 procedures after discussion with and approval of the investigator. If participants are furloughed during the washout period, they should return to the clinic on Day 14 for scheduled assessments prior to initiating the next period.

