Part 2 of the study will consist of a screening period, a check-in visit (Day -2), a baseline visit (Day -1), and 4 sequential treatment periods. Prior to dosing on Day 1 of Period 1, participants will be randomly assigned to a treatment sequence.

Participants will receive treatments in 1 of the 12 following sequences:

Sequence	Period 1	Period 2	Period 3	Period 4
1	T	ST	P	M
2	ST	M	T	P
3	P	T	M	ST
4	M	P	ST	T
5	ST	P	T	M
6	P	M	ST	T
7	T	ST	M	P
8	M	T	P	ST
9	P	T	ST	M
10	T	M	P	ST
11	ST	P	M	T
12	M	ST	T	P

Treatment T: Therapeutic dose of GSK3640254 (100 mg once daily) Days 1 through 7.

Treatment ST: Supratherapeutic dose of GSK3640254 (to be determined from Part 1) Days 1 through 7.

Treatment P: Placebo for GSK3640254 Days 1 through 7.

Treatment M: Moxifloxacin; GSK3640254 placebo Days 1 through 6 and a single dose of Moxifloxacin (400 mg) on Day 7.

To maintain the blind, the number of tablets administered for therapeutic, supratherapeutic, (Days 1 through 6 only), and placebo doses will be identical. The total number of tablets will be based on the actual supratherapeutic dose derived from Part 1 of the study. For example, if the supratherapeutic dose is determined to be 500 mg QD, the therapeutic dose would consist of one 100 mg GSK3640254 tablet and four placebo tablets, the supratherapeutic dose would consist of five 100 mg GSK3640254 tablets, and the placebo dose would consist of five placebo tablets.

Continuous Holter ECG monitoring will be performed on Day -1 (full set of replicates mirroring pre- and post-dose time points). In each treatment period, continuous Holter ECG monitoring will be performed pre-dose on Day 1, and pre-dose and up to 24 hours after dosing on Day 7.

Pharmacokinetic blood samples for the analysis of GSK3640254 and moxifloxacin will be collected at selected time points pre-dose and up to 24 hours after the Day 7 morning dose.

Safety and tolerability will be assessed by monitoring and recording of AEs, clinical laboratory results, vital sign measurements, safety 12-lead ECG results, and physical examination findings.

Study assessments will be performed as indicated in the SoA (Section 1.3). Study participants will be confined to the clinic starting on Day -2 of Period 1. Final discharge will be on Day 9 of Period 4. The total duration of the study for a participant in Part 2, including screening, is approximately 82 days.

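### No scheduled C-SSRS falls on a Part 2 dosing day, so the questionnaire trigger in Section 7.1.3 cannot interrupt a supratherapeutic course

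*Protocol*

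**What the plan says.** Section 2.3 explains that psychiatric events with an earlier maturation inhibitor led to the C-SSRS safeguard, and continues: "Participants will also be required to provide response to the C-SSRS during the on-treatment portion of the study". It points to Sections 1.3 and 8.2.5 and does not limit the commitment to Part 1. Section 8.2.5 promises repeat assessments in the treatment phase, and the risk table in Section 2.3.1 promises them across the study. Section 7.1.3 makes a confirmed positive response in the treatment phase the trigger for an immediate assessment of suicidality.

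The timing is in the two tables of Section 1.3:

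- Part 1, row "Columbia-Suicide Severity Rating Scale": Days -2, 2, 4, 6 and 8.
- Part 2, row "Columbia Suicide Severity Rating Scale": Day -2, a printed D8 in the washout column of Periods 1 to 3, and one mark in the Period 4 follow-up columns.

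Part 2 dosing fills the first seven days of every period. For the supratherapeutic arm, Section 4.1 has: "Treatment ST: Supratherapeutic dose of GSK3640254 (to be determined from Part 1) Days 1 through 7". A Part 2 footnote in Section 1.3 adds: "Participants may be furloughed during the washout portion of the respective period following Day 8 procedures".

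**The concern.** Someone who follows the reference from Section 2.3 to the Part 2 schedule finds no C-SSRS on any day when drug is given. Part 1 has three such days, and the Protocol gives no reason for the difference.

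Part 2 is also the setting that motivated the safeguard. Section 2.2.1 reports two psychiatric serious adverse events at supratherapeutic doses of a structurally similar compound in a thorough QT study. One was suicidal and homicidal ideation, which the C-SSRS addresses. The other was acute psychosis, which it does not. Section 2.2.1 also says that neither finding has been reproduced with GSK3640254. However, multiple dosing in the completed healthy-volunteer studies stopped at 320 mg daily (Section 2.2), while Part 2 aims for higher exposure.

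What is at stake is whether the suicide-specific instrument can prompt action while doses can still be withheld. The QTc analysis is not affected.

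**Working it through.** **Schedule, by column position**

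| | C-SSRS marks | On dosing days |
|---|---|---|
| Part 1 | D-2, D2, D4, D6, D8 | 3 of 7 |
| Part 2, Periods 1 to 3 | D-2 (before Period 1 only), D8 of each period | 0 of 21 |
| Part 2, Period 4 | one follow-up mark, D8 or D9 | 0 of 7 |

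Column alignment in the extracted tables is imperfect, so I checked whether it matters. The D8 entry for Periods 1 to 3 is printed text. The Period 4 mark counts to D9, or to D8 if that page carries an extra blank column; both follow the last dose. If the on-study Part 1 marks slipped one column left they would be D1, D3, D5 and D7; one column right, D3, D5, D7 and D9. At least three would still fall on dosing days.

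**Dosing days without a scheduled C-SSRS in Part 2**

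- All: 4 periods × 7 = 28.
- On GSK3640254 (T and ST): 2 × 7 = 14.
- Supratherapeutic: 7. These are the days that match the motivating events.

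**First dose of a period to its first C-SSRS**

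- Part 1: D1 to D2 = 1 day.
- Part 2, Periods 1 to 3: D1 to D8 = 7 days.
- Part 2, Period 4: 7 or 8 days.

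**Participants whose supratherapeutic course comes last.** The Section 4.1 sequence table has ST in Period 4 of sequences 3, 8 and 10. With equal allocation to the 12 sequences:

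- Randomized: 42 ÷ 12 × 3 = 10.5.
- Completers: 34 ÷ 12 × 3 = 8.5.

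**Exposure.** Section 4.3 targets a steady-state Cmax of about 4.4 µg/mL. Section 2.2.5.1 gives 2154 ng/mL for 320 mg on Day 14. The ratio is 4.4 ÷ 2.154 ≈ 2.0.

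**Which dosing day is free.** The safety ECG note in the Part 2 table reads: "On Days 1, 4, and 7, ECGs will be collected at pre-dose and post-dose at 1, 2, 3, 4, 6, and 24 hours". The 24-hour tracings after Days 1 and 4 fall on Days 2 and 5, so Day 3 has no safety ECG. Pre-dose PK samples are on Days 1, 5, 6 and 7, and Holter recording is on Days 1 and 7 (to Day 8). Day 3 therefore has none of the three.

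**Would Day 3 or 4 be too early?** Section 2.2.3 states: "The mean half-life ranged from approximately 22 to 28 hours". As a one-compartment approximation, the fraction of steady state after n daily doses is 1 − 2^(−24n/t½), with t½ from 28 to 22 h:

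- n = 3: 1 − 2^(−72/28) = 0.83 to 1 − 2^(−72/22) = 0.90, with 4 dosing days left.
- n = 4: 1 − 2^(−96/28) = 0.91 to 1 − 2^(−96/22) = 0.95, with 3 dosing days left.

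**The case against.** The strongest reply is that the schedule is coherent and breaks no promise. The risk table in Section 2.3.1 divides mitigation into screening and on-treatment, so the Section 2.3 sentence can mean any time after screening. D8 of Periods 1 to 3 lies between the first and last doses of the crossover, about 24 hours after a dose of a drug with a half-life near one day. Section 8.2.5 makes each questionnaire look back to the previous one, so D8 covers the dosing week. It also precedes any furlough and the next period, which a positive answer can block. This stands: a reader might infer a flat contradiction between Section 2.3 and the schedule, but the documents do not support one.

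A reader might also infer that participants are unprotected while being dosed. That is not supported either. They are questioned before each dose (Section 8.3.2), are housed in the clinic, and can be stopped for newly emerging suicidal ideation or a Grade 3 psychiatric event however it is detected (Section 7.1.4). The gap concerns the questionnaire only. However, open-ended adverse event questioning is not suicide-specific and is not the instrument that Section 2.3 names.

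Closer monitoring of a sentinel cohort is ordinary practice, and the Part 2 dose may not exceed what Part 1 tested (Sections 4.3 and 6.6). That could explain the difference between the Parts, but the Protocol does not say so. Part 1 also exposes only 6 participants per cohort, at most 12, to active drug.

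Finally, no check made after the last dose can stop dosing. This is true of any end-of-treatment assessment, and it is why at least one earlier check is useful.

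**Conclusion.** The point holds as an inexpensive safety improvement. In Part 2 no scheduled C-SSRS falls on any of the 28 dosing days, including the 7 supratherapeutic ones, against three on 7 dosing days in Part 1. A scheduled questionnaire therefore cannot set off the Section 7.1.3 assessment before a period's course is complete. For about 10.5 of 42 randomized participants (8.5 of 34 completers) the check following the supratherapeutic course comes after their last dose in the study.

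The counts assume the table alignment described above and equal allocation across sequences. The 10.5 further assumes that all randomized participants reach Period 4. No rate of psychiatric events is claimed for GSK3640254.

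**What to change.** Add one C-SSRS to every Part 2 period on Day 3. Day 4 after the 6-hour safety ECG is the alternative, and is also a Part 1 C-SSRS day. Give it in all four periods so that the schedule does not reveal treatment; the moxifloxacin period is placebo on those days. Keep the D8 and Period 4 follow-up assessments.

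Add a sentence to Section 5.3.3 allowing the questionnaire outside ECG windows, because its limit on stimulating conversation can be read as running from Day 1 to 24 hours after the Day 7 dose. If post-dosing assessment alone is intended in Part 2, Section 2.3 should say so and give the reason.

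The cost is a schedule amendment and 4 questionnaires per participant, or 4 × 42 = 168 in all. At an assumed 5 to 10 minutes each, that is 20 to 40 minutes per participant over the study. Participants are already confined on these days, and the site already administers the instrument.
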